11.4. PK and PD Assessments

PK samples will be shipped to PPD Global Central Labs. Details of the procedures to be followed for sample collection, storage, and shipment will be documented in a separate PK Laboratory Manual.

The following PK and PD assessments will be performed on the visit days specified in [Table 1](#) and [Table 2](#) to determine the safety profile of RPC1063:

- Standard PK sampling: PK samples are to be taken predose and 6-8 hours after dosing on Day 1. Samples on study will either be trough samples, taken prior to dose administration or will be collected 2 to 6 hours after dose administration, as indicated in the Schedule of Events footnotes.
- Stool culture for fecal biomarkers – fecal lactoferrin and calprotectin, which are tests sensitive to the identification of intestinal inflammation
- Plasma protein biomarker analysis (cytokines, chemokines, other inflammatory proteins)
- Total Igs: IgA, IgG, IgM

11.5. Monitoring of Patients With Adverse Events of Special Interest

Several of the AEs noted in fingolimod clinical studies may be a consequence of S1P₁ stimulation and will therefore be closely monitored in the RPC01-202 study. These AEs include:

- a. Bradycardia and heart conduction abnormalities. Dose-related transient, reversible bradycardia and first degree atrioventricular block were reported primarily as first dose effects in fingolimod studies. The HR reduction observed with sphingosine-1-receptor agonists is an expected effect of S1PR modulation and appears to be conducted through the same pathway as vagus nerve stimulation. In addition, these negative chronotropic effects of S1P₁ agonists appear to attenuate over time secondary to S1PR desensitization and internalization on cardiac myocytes ([Kovarik 2008](#)). This effect appears to occur with increasing exposure to investigational drug; thus, gradual dose escalation of the dose of RPC1063 over several days may mitigate against larger reductions in HR.
- b. Pulmonary toxicity. An initial sharp decrease followed by a slow progressive decline over time in FEV1 was observed in fingolimod clinical studies. Nonclinical toxicity studies with RPC1063 have revealed the potential for pulmonary toxicity at doses considerably higher than the pharmacologically active dose. Pulmonary function tests including FEV1, FVC, and DLCO, if applicable, will be measured in all patients. All efforts should be made to obtain DLCO assessments and exceptions based on lack of equipment must be pre-approved by the Sponsor. Every patient whose PFTs are abnormal will be followed until such time as resolution is confirmed or no further improvement is expected by the Investigator (based on a follow-up period of not less than 3 months).
- c. Hepatotoxicity. Fingolimod caused frequent, reversible liver enzyme elevations greater than 3-fold above the ULN in up to 12% of patients; this was a significant cause of cessation of therapy. In this study, clinical blood chemistry analyses to assess LFTs will be performed. Every patient whose LFTs are abnormal will be followed until values return to baseline.
- d. Macular edema. Instances of serious macular edema were reported in fingolimod renal transplant studies, and a 0.8% incidence was reported as an SAE in fingolimod

- (1.25 mg dose) MS clinical studies. Nonclinical studies with RPC1063 have not revealed eye-related toxicities. In this study, OCT will be performed in all patients at baseline and the end of study visits or early termination. In addition, patients will be questioned about visual signs or symptoms at each study visit and instructed to inform the investigator if they develop symptoms between visits. For patients with symptoms of macular edema, OCT and ophthalmologic examination including dilated ophthalmoscopy will also be performed. Every patient whose ophthalmic evaluations reveal abnormalities will be followed until values return to baseline.
- e. Opportunistic or serious infections. TB, serious bacterial infections, systemic fungal infections, viral infections such as herpes infections (including herpes zoster and disseminated herpes simplex) and protozoal infections should be reported as adverse events of special interest.

Overall, the following procedures should be followed:

- Vital signs will be assessed in supine and standing position at every visit. A sudden, significant fall in BP (> 20 mmHg) between 2 and 5 minutes after standing from the supine position will be interpreted as orthostatic hypotension and will be documented in the patient chart and eCRF.
- Patients will be closely monitored in the clinic after their first dose of the initial dose escalation regimen for a period of 6 hours after treatment. ECGs will occur predose and at Hour 6 following dosing, with more frequent assessments as clinically indicated; vital signs, including orthostatic BP assessment, will be assessed predose and then hourly for 6 hours following dosing.
- Clinicians should be particularly mindful of patients who have a low HR at baseline (spontaneously or through drug induced β -receptor blockade), prior to administration of the investigational drug. Atropine IV is recommended as the first line treatment of bradycardia, up to a maximum daily dose of 3 mg. Furthermore, the common guidelines for treatment of bradycardia (e.g., Advanced Cardiac Life Support-ACLS guidelines) should be followed as appropriate:
 - In case of clinical symptoms or hypotension, administration of atropine 1 mg, repeated administration in 3-5 minutes.
 - If HR and/or BP remain unresponsive, consider administration of dopamine drip 5-20 μ g/kg/min or epinephrine drip 2-10 μ g/min.
 - Performance of transcutaneous pacing may also be considered
 - In the setting of decreased BP, isoproterenol should be avoided or used with caution.
- Any condition that might affect the outcome of pulmonary function testing including infection, respiratory symptoms, occupational exposures (including asbestos) and cigarette smoking needs to be collected before PFT testing and transcribed to the pulmonary function tests eCRF page. If patients have decline in PFT values (FEV_1 and/or FVC) below 50% of the predicted values, treatment should be discontinued. If a patient discontinues due to respiratory AE, the Investigator should ensure that the

- patient has adequate evaluations as clinically indicated by a pulmonologist (consider PFTs, chest X-ray or high resolution computed tomography, based on findings of the other exams) at the time of the AE. For patients with pulmonary nodules, lung biopsy should be considered (*Cryptococcus* pneumonia and pulmonary TB have been reported with fingolimod). Further evaluations will be conducted until such time as resolution is confirmed or no further improvement is expected by the Investigator (based on a follow-up period of not less than 3 months).
- If patients have elevations in LFTs (ALT or/and AST) greater than 3 times the ULN, a retest should be performed within 14 days whenever possible. Upon confirmation of the abnormality, retests should be performed weekly until the elevated LFT decreases below 3 times the ULN. If the LFTs increase is confirmed to be above 5 times the ULN the investigational drug must be permanently discontinued.
 - Study drug must be discontinued in any patient who has a diagnosis of macular edema. Patients with a diagnosis of macular edema must be followed up monthly or more frequently if needed based on the ophthalmologist's judgment. Further ophthalmological evaluations will be conducted until such time as resolution is confirmed or no further improvement is expected by the ophthalmologist (based on a follow-up period of not less than 3 months). If the patient does not show definite signs of improvement on examination 6 to 8 weeks after discontinuation of investigational drug, then therapy for macular edema in conjunction with an ophthalmologist experienced in the management of this condition should be initiated.
 - Examination of the skin for lesions will be performed as part of the physical examination at screening and at the end of study. If skin lesions are noted, the patient will be referred to a dermatologist for evaluation and follow-up care.

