12.5. Procedures to be followed in the Event of Abnormal Laboratory Test Values

In the event of unexplained abnormal laboratory test values, the tests should be repeated immediately and followed up until they have returned to the normal range and/or an adequate explanation of the abnormality is found. For abnormal laboratory test values related to AEs of special interest, refer to Section 11.5.

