12.6. Clinical Laboratory Parameters and Abnormal Laboratory Test Results

Clinically significant changes, in the judgment of the Investigator, in laboratory parameters (abnormalities) will be recorded as AEs.

During the treatment period, all Total WBC and WBC differential results will be blinded. Reductions in ALC levels is a known pharmacodynamic effect of RPC1063. If any of the following results are observed, the Investigator will be notified and asked to repeat the laboratory tests within approximately 7 days:

- Absolute lymphocyte count [ALC] < 200 cells/ μ L
- Absolute neutrophil count [ANC] < 1000 cells/ μ L
- Total WBC > 20,000 cells/ μ L

If the repeat values also exceed these limits, the Investigator will be informed that the patient's results for the abnormal parameter have fallen below the acceptable threshold.

If ANC or total WBC counts are confirmed below the acceptable limits, the Medical Monitor will contact the treating investigator to request close monitoring for risk of serious infection and appropriate follow-up, at the discretion of the investigator.

If the ALC is confirmed < 200 cells/ μ L, the Investigator will temporarily discontinue investigational drug and then consult with the Medical Monitor. Laboratory testing will be repeated weekly until ALC is > 500 cells/ μ L.

When ALC has returned to > 500 cells/ μ L, the treatment may be reinitiated at the Investigator's discretion (Section 9.6.2 for instructions on resuming treatment after missing doses). For patients whose ALC level is confirmed < 200 cells/ μ L and has not reached the acceptable range (ALC > 500 cells/ μ L) during the study, laboratory testing will be repeated at the 90-day Safety Follow-up Visit.

If patients have elevations in ALT and/or AST \geq 3x the upper limit of normal (ULN), a retest should be performed as soon as possible but not later than 14 days after the original test. If the abnormality is confirmed, weekly testing should continue until ALT and AST are < 3x ULN. If the ALT and/or AST stabilizes at a level > 3x ULN, the Medical Monitor may agree to less

frequent testing. The Investigator should establish causality. In addition, the confirmed elevation $> 3x$ ULN is an adverse event of special interest (see Section 11.5) and should be reported by the Investigator.

At any time, if any of the following occur and there are no apparent alternative causes for the finding, the investigational drug must be permanently discontinued:

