- ALT or AST $> 8x$ ULN or
- ALT or AST $> 5x$ ULN with confirmation, within 2 weeks or
- ALT or AST $> 3x$ ULN and (total bilirubin $> 2x$ ULN or INR > 1.5) or
- ALT or AST $> 3x$ ULN with the appearance of fatigue, nausea, vomiting, right upper quadrant pain or tenderness, fever, rash, and/or eosinophilia ($>5\%$).

The Investigator should establish causality.

After discontinuation due to elevation of ALT or AST $> 5x$ ULN or concurrent elevations of ALT or AST $> 3x$ ULN and bilirubin $> 2x$ ULN, further liver function evaluation should be performed (for example, coagulation panel and alkaline phosphatase) in consultation with the Medical Monitor.

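### For ALT or AST confirmed above 5 times ULN with an apparent alternative cause, Protocol Sections 11.5 and 12.6 disagree on whether permanent discontinuation is mandatory

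*Protocol*

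**What the plan says.** Two sections of the protocol state a stopping rule for raised liver enzymes.

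- **Section 11.5** (Monitoring of Patients With Adverse Events of Special Interest) uses LFTs to mean ALT and/or AST. Its stopping rule reads: "If the LFTs increase is confirmed to be above 5 times the ULN the investigational drug must be permanently discontinued". For values above 3 times ULN it says that "a retest should be performed within 14 days whenever possible", followed by weekly retests until the value is below 3 times ULN.
- **Section 12.6** (Clinical Laboratory Parameters and Abnormal Laboratory Test Results) introduces a list of four triggers with: "if any of the following occur and there are no apparent alternative causes for the finding, the investigational drug must be permanently discontinued". One of the four is "ALT or AST $> 5x$ ULN with confirmation, within 2 weeks". For values at or above 3 times ULN it says that "a retest should be performed as soon as possible but not later than 14 days after the original test". It also asks for weekly testing, but lets the Medical Monitor agree to less frequent testing if values settle above 3 times ULN.

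Between them, Section 12.5 directs the reader as follows: "For abnormal laboratory test values related to AEs of special interest, refer to Section 11.5".

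**The concern.** Both sections say in mandatory terms that the drug must be stopped for good, and both apply this to a confirmed ALT or AST above 5 times ULN. Only one makes it depend on cause. An investigator whose patient has such a rise and a plausible other explanation gets a different answer from each section.

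What is at stake is uniform conduct of a patient-safety rule. The protocol plans about 80 centers and an open-label period of up to 6 years, so many investigators will read these sections separately. AEs leading to discontinuation of drug are a safety endpoint (Protocol Section 8.2.2) and a planned summary (SAP Section 6.20.1). If sites work from different sections, that count partly reflects which section was read.

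**Working it through.** No arithmetic applies; the check is a comparison of the texts.

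**1. Do the sections cover the same event?** Yes. Both concern ALT or AST above 5 times ULN with confirmation. Section 9.1.2.1 lists LFT elevation among the AEs of special interest, which is the subject of 11.5, and 12.6 itself treats a confirmed elevation above 3 times ULN as such an event.

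**2. What does each section require?** Take ALT or AST above 5 times ULN, confirmed within 2 weeks. The time limit is fixed here because 12.6 sets it and the 11.5 stopping sentence does not.

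| Case | Section 11.5 | Section 12.6 | Result |
|---|---|---|---|
| No apparent alternative cause | Stopping mandatory | Stopping mandatory | Agree |
| Apparent alternative cause | Stopping mandatory | Stopping not made mandatory | Conflict |

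The other three triggers in 12.6 do not remove the conflict in the second row, because all four sit under the same condition on cause.

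**3. Does any other text settle it?**

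- Section 12.5 points to 11.5 for laboratory values related to AEs of special interest and does not mention the condition in 12.6.
- Section 12.6 refers back to 11.5 only for treating and reporting confirmed elevations above 3 times ULN as AEs of special interest.
- Section 9.7.1, on discontinuing treatment, contains no liver-test rule.
- SAP Section 6.20.6 tabulates liver tests by multiples of ULN and gives no stopping rule.

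No visible passage ranks the two sections.

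**4. Secondary wording differences.**

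| Item | Section 11.5 | Section 12.6 |
|---|---|---|
| Retest trigger | Greater than 3 times ULN | At least 3 times ULN |
| Retest timing | 14 days, where possible | 14 days as an outer limit |
| Retest frequency | Weekly until below 3 times ULN | Weekly, but less often by Medical Monitor agreement if stable above 3 times ULN |

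The trigger difference affects only a value of exactly 3 times ULN. The timing difference is one of strictness, since both use 14 days. The frequency difference concerns monitoring, not stopping.

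**5. The further triggers in 12.6.** These are ALT or AST above 8 times ULN; above 3 times ULN with raised bilirubin or INR; and above 3 times ULN with listed symptoms or eosinophilia. Section 11.5 neither states nor excludes them, so both lists can be applied together. However, a reader sent to 11.5 by Section 12.5 would not see them.

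**The case against.** The best reply is that both sections are in force, that 12.5 already directs the reader to 11.5, and that an investigator can comply with both by stopping whenever either requires it. Part of this stands. Section 12.6 does not forbid stopping, and Section 9.7.1 separately lets the investigator stop drug in the patient's interest. But the reply does not settle the matter. Section 12.6 follows the cross-reference with its own rule for the same finding, and its condition on cause would have no effect at this threshold if 11.5 always governed. The text does not say whether that was intended.

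Three stronger readings are tempting, and the documents do not support them.

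- **A reader might infer that 12.6 allows the patient to continue.** It says when stopping is required and is silent on the remaining cases. The conflict is over what is mandatory, not an order to stop against permission to go on. Nor is 11.5 free of all conditions: it still requires confirmation.
- **A reader might count the three further triggers as contradictions.** They add to 11.5. The difficulty is only that they are easy to miss.
- **A reader might infer an effect on the primary endpoint**, since missing scores count as nonresponse and one patient in an arm of about 60 is 1/60 = 1.7 percentage points. The chain is not established:
  - After Day 1, induction chemistry is scheduled only at Weeks 4 and 8 (Protocol Table 1). A rise first seen at Week 8 would be confirmed later, when the Week 8 assessments would normally be done.
  - Patients who stop drug without withdrawing consent are asked for an Early Termination visit (Section 9.7.1), which includes endoscopy and the full Mayo score (Table 1).
  - SAP Section 6.4 counts missing scores as nonresponse, and the discontinuation limb of the treatment-failure rule in SAP Section 6.19 covers lack of effect, not an AE.
  - The 1.7 points also requires that the patient would otherwise have been in remission.

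**Conclusion.** The contradiction is real and narrow. It concerns patients with ALT or AST confirmed above 5 times ULN who have an apparent alternative cause. For them, permanent discontinuation is mandatory under Protocol Section 11.5 and not made mandatory under Section 12.6, with no stated precedence. The retest differences are minor but belong in the same correction.

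The number of patients affected cannot be derived. The documents give no rate for confirmed rises above 5 times ULN, still less for those with another explanation. The figure in Section 11.5 of up to 12% is for a different drug and a lower threshold (3 times ULN), so it cannot serve as an estimate. The demonstrated consequence is possible inconsistency between sites in applying a safety stopping rule, and hence in the counts of AEs leading to drug discontinuation. No effect on the primary endpoint is shown, and sample size, power and type I error are untouched.

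The conclusion assumes that no redacted or removed text ranks the two sections.

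**What to change.** Sections 11.5 and 12.6 must be reconciled into one liver-test rule, held in one place and cross-referenced from 11.5, 12.5 and 12.6. The single text should state:

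- whether mandatory stopping depends on cause;
- the full list of triggers;
- what counts as confirmation, including any time limit;
- the retest trigger, deadline and frequency, and any exception to the frequency.

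Which version of each applies is a clinical decision for the sponsor's team, and this review takes no position on it.

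The cost is protocol wording in one amendment, with the usual regulatory and ethics approval. The planned SAP tables need no change.

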12. SAFETY DEFINITIONS, MONITORING, AND REPORTING

Throughout the study, the Investigator will remain alert to possible AEs. If an AE occurs, the first concern should be for the safety of the patient, and appropriate medical intervention should be provided if necessary.

At the signing for the informed consent form, patients should be given names and telephone numbers of site staff for reporting AEs and medical emergencies.

12.1. Adverse Events

The AE definitions and reporting procedures provided in this protocol comply with current CFR 21 Part 312.32. An AE is any untoward medical occurrence that does not necessarily have a causal relationship with the investigational medicinal product. An AE can therefore be any unfavorable or unintended sign, including an abnormal laboratory finding, symptom or disease temporally associated with the use of an investigational medicinal product whether or not considered related to the investigational medicinal product.

UC disease relapse and related symptoms will be monitored as study endpoints, but will not be recorded as AEs.

AEs will be monitored throughout the entire study including the 90-day Safety Follow-up Visit. Investigators will ask the patient at each visit if they have experienced any untoward occurrence since the last study visit. All AEs will be recorded on the eCRFs provided: a description of the event, severity, time of occurrence, duration, any action (e.g., treatment and follow-up tests), and the outcome should be provided along with the Investigator's assessment of the relationship to the investigational drug.

AEs will be recorded from the time written informed consent is signed until 90 days following the last dose of treatment with the investigational drug.

If known, the event diagnosis should be recorded, in preference to the listing of individual signs or symptoms. AEs must be graded as being mild, moderate, or severe and their approximate duration given. Definitions of severity are as follows:

Mild: an AE usually transient in nature and generally not interfering with normal activities;

Moderate: an AE that is sufficiently discomforting to interfere with normal activities;

Severe: an AE that is incapacitating and prevents normal activities.

Even if the Investigator feels there is no relationship to the investigational drug, all AEs MUST be recorded in the eCRF. The Investigator is requested to assess the relationship of any AEs to treatment using the following definitions:

Unrelated: those AEs which are clearly and incontrovertibly due to extraneous causes (concurrent drugs, environment etc.) and do not meet the criteria for drug relationship listed under Unlikely, Possible, Probable or Related.

Unlikely: an AE may be considered unlikely if it includes at least the first two features:

- It does not follow a reasonable temporal sequence from administration of the drug.

- It could readily have been produced by the patient's clinical state, environmental or toxic factors, or other modes of therapy administered to the patient.
- It does not follow a known pattern to the suspected drug.
- It does not reappear or worsen when the drug is re-administered.

Possible: an AE may be considered possible if it includes at least the first two features:

- It follows a reasonable temporal sequence from administration of the drug.
- It could readily have been produced by the patient's clinical state, environment or toxic factors, or other modes of therapy administered to the patient.
- It follows a known response pattern to the suspected drug.

Probable: an AE may be considered probable if it includes at least the first three features:

- It follows a reasonable temporal sequence from administration of the drug.
- It could not be reasonably explained by the known characteristics of the patient's clinical state, environmental or toxic factors or other modes of therapy administered to the patient.
- It disappears or decreased on cessation or reduction in dose. There are exceptions when an AE does not disappear upon discontinuation of the drug (e.g., bone marrow depression, fixed drug eruptions, tardive dyskinesia, etc.).
- It follows a known pattern of response to the suspected drug.

Related: an AE may be considered related if it includes all of the following features:

- It follows a reasonable temporal sequence from administration of the drug.
- It could not be reasonably explained by the known characteristics of the patient's clinical state, environmental or toxic factors or other modes of therapy administered to the patient.
- It disappears or decreased on cessation or reduction in dose. There are exceptions when an AE does not disappear upon discontinuation of the drug (e.g., bone marrow depression, fixed drug eruptions, tardive dyskinesia, etc.).
- It follows a known pattern of response to the suspected drug.
- It reappears or worsens if the drug is re-administered.

